## Objective

The objective of this study is to assess the intervention effect of the three groups in any of the subgroups according to sex, age, use of paracetamol and/or NSAID prior to surgery, ASA-score, type of anesthesia, level of pain at rest prior to surgery and level of pain when active prior to surgery.

## Subgroups

The subgroups are dichotomized based on the following pre-randomization patient characteristics:

- Sex (male *versus* female)
- Age ( $\leq 65$  years *versus*  $> 65$  years)
- ASA group (ASA I and II *versus* III)
- Preoperative pain at rest measured using visual analogue scale (VAS) ( $\leq 30$  mm *versus*  $> 30$  mm)
- Preoperative pain when active measured using VAS ( $\leq 30$  mm *versus*  $> 30$  mm)
- Type of anesthesia (spinal anesthesia *versus* general anesthesia and converted to general anesthesia)
- Prior daily use of paracetamol and/or NSAID (either paracetamol or NSAID *versus* neither)

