## Statistical methods

Statistical analyses will be carried out using R (R Core Team, Vienna, Austria) and Stata (StataCorp LLC, Texas, USA) by two independent statisticians ([name] and [name]). The two statisticians will independently prepare a statistical report, which will be compared for any discrepancies. The discrepancies will be logged, and any changes for the final report will be described. The final report, the two original reports, and the discrepancies log, will be approved by the co-authors. All reports will be added as supplemental material in the final paper.

We will perform pairwise comparisons of the three groups, i.e., three comparisons. We plan to test for subgroup heterogeneity of the intervention effect by assessing whether the interaction between the subgroup and the treatment group is significantly different. We will use quantile regression adjusted for site to test for significant interaction between the predefined dichotomized subgroups and treatment group using a threshold of 0.05 for subsequent Wald test.

We will assess the effects of dexamethasone for each of the predefined subgroups analyzed separately using van Elteren test adjusted for site. As these subgroup analyses will be interpreted as exploratory, and with the purpose of generating hypotheses, we will use the same threshold for significance as used in the main trial. The threshold for significance will therefore be multiplicity corrected using Bonferroni correction and is based on the three groups. Thus, the level of significance will be 0.017. We will quantify and report differences between the groups using Hodges-Lehmann median difference and the corresponding 98.3% confidence intervals.

The subgroup analyses will be presented in forest plots.

Attached is an example of the planned analyses for one subgroup analysis (**Supplemental Material**)

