#### Further information

- Clinicaltrials.gov identifier for the main trial: NCT03506789
- Clinicaltrials.gov identifier for this subgroup analyses: NCT05008367
- Published protocol article for the main trial: <https://doi.org/10.1111/aas.13481>
- Published statistical analyses plan for the main trial: <https://doi.org/10.1111/aas.13560>

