## Simulated data

```
#Number of participants
n_part <- 485
df <- NULL

#Random assignment to the three groups
df$group <- as.factor(sample(c(1:3),n_part, replace=TRUE))

#Random assignment to the sites
df$site <- sample(c("A","B","C"),n_part, replace=TRUE)

#Random assignment to age
df$bc_age <- rnorm(n_part, mean=65, sd=8)
df$bc_ASA_above_2 <- sample(c(0,1),n_part, replace=TRUE)
df$bc_High_pain_at_rest <- rnorm(n_part, mean=30, sd=10)
df$bc_High_pain_when_active <- rnorm(n_part, mean=30, sd=10)
df$bc_Only_spinal <- sample(c(0,1),n_part, replace=TRUE)
df$bc_Prior_pain_med <- sample(c(0,1),n_part, replace=TRUE)
df$bc_BMI <- rnorm(n_part, mean=30, sd=4)

df <- data.frame(df)
df$age <- 0
df$age[df$bc_age > 65] <- 1

df_mc <- df

#The simulated outcome depending on the median for each group:
n_dd <- 35
n_dp <- 38
n_pp <- 43
df$outcome[df$group==1] <- rnorm(sum((df$group==1)*1),mean=n_dd,sd=5)
df$outcome[df$group==2] <- rnorm(sum((df$group==2)*1),mean=n_dp,sd=5)
df$outcome[df$group==3] <- rnorm(sum((df$group==3)*1),mean=n_pp,sd=5)

#The simulated RRR of age:
rrr_age <- 0.1
df$outcome[df$age == 1] <- df$outcome[df$age == 1]-df$outcome[df$age == 1]*rrr_age
```

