## Baseline characteristics for subgroup

```
library(tableone)
CreateTableOne(c("bc_age", "bc_BMI", "bc_ASA_above_2", "bc_High_pain_at_rest", "bc_High_pain_when_active",
                "bc_Only_spinal", "bc_Prior_pain_med"), strata = c("age", "group"),
              factorVars = c("bc_ASA_above_2", "bc_Only_spinal", "bc_Prior_pain_med"),
              data=df, test=FALSE)
```

```

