##  bc_Only_spinal = 1 (%)           38 (46.9)  36 (47.4)
##  bc_Prior_pain_med = 1 (%)         39 (48.1)  34 (44.7)
##                               Stratified by age:group
##                               0:2           1:2
##  n                               71           78

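### Type of anesthesia is listed as a pre-randomization factor but is defined by the anesthesia finally received, and the documents do not show that this was fixed before randomization

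*Combined protocol and SAP*

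**What the plan says.** The Subgroups section opens with one timing statement that covers every factor: "The subgroups are dichotomized based on the following pre-randomization patient characteristics". Seven factors follow. For type of anesthesia, one level is spinal and the other is "general anesthesia and converted to general anesthesia".

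The Objective section names the same factors. It places analgesic use and both pain measures before surgery but gives anesthesia no time reference: "type of anesthesia, level of pain at rest prior to surgery and level of pain when active prior to surgery".

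In the supplemental example, the Simulated data section creates a two-level variable, "df$bc_Only_spinal <- sample(c(0,1),n_part, replace=TRUE". It is then tabulated as "bc_Only_spinal = 1" in the table titled "Baseline characteristics for subgroup".

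Under Statistical methods, each factor enters a treatment-by-subgroup interaction test at 0.05. Each stratum is also analysed separately, with van Elteren tests and Hodges-Lehmann differences at the 0.017 level. The section gives the status of the stratum-level analyses: "As these subgroup analyses will be interpreted as exploratory, and with the purpose of generating hypotheses".

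**The concern.** The plan sets its own criterion, that a subgroup must be known before randomization. It then fills one stratum partly according to an event during anesthesia care. Of the seven factors, this is the only one defined by such an event.

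The criterion matters because it lets a reader treat the arms within a stratum as randomized groups. If conversion took place after allocation, and either its frequency or the kind of patient who converts depended on arm, the arms within the spinal and general strata would no longer be comparable. The interaction test and all the stratum-level comparisons for this factor would be exposed. Analysing all randomized participants would not repair this, because the problem would lie in how patients are sorted into strata, not in who is included.

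**Working it through.** The plan gives no figure on this point, so the check is mainly one of reading.

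**1. What defines the stratum.** Under Subgroups, converted patients are counted with general anesthesia. Spinal is the only other type listed, so I read these as patients who began with, or were intended for, spinal. Their stratum follows what they finally received. The variable name in the example, which implies spinal and nothing else, fits this reading.

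**2. What fixes the timing.** The sections that could settle it are:

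- Subgroups: a general label over all seven factors, with no separate statement for anesthesia.
- Objective: a time reference for analgesic use and pain, none for anesthesia.
- Population and Statistical methods: no order of events, and no rule on planned versus received anesthesia.
- Supplemental example: the variable sits in a baseline table, but its values are a random 0/1 draw and the worked subgroup is age. It is not evidence on timing.
- Further information: a link to the "Published protocol article for the main trial", which may give the order of events but is not among the documents.

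The label is therefore the only timing statement.

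**3. What follows in each case.**

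| Order of events | Conversion related to arm? | As-received strata | Strata by type planned before randomization |
|---|---|---|---|
| Conversion before randomization | Cannot be | Fair, label correct | Fair |
| Conversion after randomization | No | Fair, label wrong | Fair |
| Conversion after randomization | Yes | Not protected by randomization | Fair |

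The documents do not say which row applies. The last column is sound in all three.

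**4. How many patients would change stratum.** This describes composition, not bias. The inputs are assumptions, apart from N = 485, which is the number in the example code and is not given as the trial's size. Let g be the share planned for general anesthesia and c the conversion rate among planned spinals. Assume that every converted patient was a planned spinal.

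- Moved = N × (1 − g) × c
- As-received general stratum = N × g + moved
- Share of that stratum moved = moved ÷ as-received general stratum

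For g = 10% and c = 5%: 485 × 0.90 × 0.05 = 21.8 moved; 48.5 + 21.8 = 70.3; 21.8 ÷ 70.3 = 31.0%.

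| g | c = 1% | c = 3% | c = 5% |
|---|---|---|---|
| 10% | 4.4 of 52.9 (8.3%) | 13.1 of 61.6 (21.3%) | 21.8 of 70.3 (31.0%) |
| 20% | 3.9 of 100.9 (3.8%) | 11.6 of 108.6 (10.7%) | 19.4 of 116.4 (16.7%) |
| 30% | 3.4 of 148.9 (2.3%) | 10.2 of 155.7 (6.5%) | 17.0 of 162.5 (10.4%) |

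So about 3 to 22 patients would move. That is 1-5% of the planned-spinal stratum (c itself) and 2-31% of the as-received general stratum.

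The example table cannot replace these assumptions. Its spinal-only counts are 38 + 36 + 36 + 35 + 41 + 42 = 228 of 81 + 76 + 71 + 78 + 86 + 93 = 485, or 47.0%, which is what a random 0/1 draw would give.

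**The case against.** The strongest reply is that no contradiction is shown. If randomization came after anesthesia was established and any conversion had happened, the definition and the label agree. This is a short secondary plan that relies on the main trial's protocol, and the order of events may be stated there. On that view one clarifying sentence is enough. It can also be said that anesthesia received is a legitimate exploratory question, and that the plan should not give it up for a bias nobody has demonstrated.

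Much of this stands:

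- Bias is not shown, and the main protocol may vindicate the label.
- Moving converted patients back to spinal gives first-started anesthesia, which is not the same as planned anesthesia. A patient planned for spinal but started on general is not recovered by that recode. First-started type is itself a baseline factor only if it was started before randomization.
- The plan names converted patients only inside a merged category, and the example variable has two levels. That they can be separated in the data is an assumption.
- The table of patients moved rests on assumed rates, and 31% is its extreme corner. It carries no weight as evidence of bias.

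The objection does not remove the point. The general label cannot establish the timing of an event it does not mention. The question about anesthesia received is also not lost, because it stays as a sensitivity analysis. A classification by planned type meets the plan's own criterion whichever order of events applies.

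**Conclusion.** The point holds in a limited form. The factor is described as pre-randomization but is defined by the anesthesia finally received, and the supplied documents do not show that this was fixed before randomization.

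A reader might go further and infer that conversion happened after allocation, so that this subgroup is biased. The documents do not support that. They do not give the order of randomization, anesthesia and conversion, and nothing in them links conversion to arm. Both conditions would be needed for bias, and its size cannot be calculated.

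The reach is small: one of seven subgroups, in analyses meant to generate hypotheses. The change is still worth making, because it closes a possible route to bias at little cost. That the timing is unstated is clear from the text. That planned type was recorded and converted patients can be identified is assumed.

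**What to change.** For the primary version of this subgroup, classify patients by the anesthesia planned before randomization, so that converted spinal patients stay in the spinal stratum. Report the as-received split as a labelled sensitivity analysis, with the number of conversions in each arm.

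First-started anesthesia may stand in for planned type only if it was started before randomization, and the plan should then say so.

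If planned type was not recorded, or converted patients cannot be separated in the data, keep the as-received split. In that case remove the pre-randomization label for this factor under Subgroups and its baseline label in the table, unless randomization is confirmed to have followed any conversion.

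The cost is a change of wording and one rebuilt variable, provided the data allow it. There are two downsides. The general-anesthesia stratum becomes somewhat smaller, by 2-31% under the assumed rates and most where planned general anesthesia is rare. The primary question also becomes one about anesthesia planned, with anesthesia received moved to the sensitivity analysis.

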## Population

We will include all randomized participants with useful data in all analyses (intention-to treat population).

## Outcome

48-hour morphine consumption as defined as the primary outcome in the original trial.

## Baseline variables

Continuous data will be presented with mean and standard deviations (SD) or median and interquartile range when appropriate; while categorical data will be presented as number and percentage.

## Statistical methods

Statistical analyses will be carried out using R (R Core Team, Vienna, Austria) and Stata (StataCorp LLC, Texas, USA) by two independent statisticians ([name] and [name]). The two statisticians will independently prepare a statistical report, which will be compared for any discrepancies. The discrepancies will be logged, and any changes for the final report will be described. The final report, the two original reports, and the discrepancies log, will be approved by the co-authors. All reports will be added as supplemental material in the final paper.

We will perform pairwise comparisons of the three groups, i.e., three comparisons. We plan to test for subgroup heterogeneity of the intervention effect by assessing whether the interaction between the subgroup and the treatment group is significantly different. We will use quantile regression adjusted for site to test for significant interaction between the predefined dichotomized subgroups and treatment group using a threshold of 0.05 for subsequent Wald test.

We will assess the effects of dexamethasone for each of the predefined subgroups analyzed separately using van Elteren test adjusted for site. As these subgroup analyses will be interpreted as exploratory, and with the purpose of generating hypotheses, we will use the same threshold for significance as used in the main trial. The threshold for significance will therefore be multiplicity corrected using Bonferroni correction and is based on the three groups. Thus, the level of significance will be 0.017. We will quantify and report differences between the groups using Hodges-Lehmann median difference and the corresponding 98.3% confidence intervals.

The subgroup analyses will be presented in forest plots.

Attached is an example of the planned analyses for one subgroup analysis (**Supplemental Material**)

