## Quantile regression for interaction only

```
#https://cran.r-project.org/web/packages/quantreg/vignettes/rq.pdf  
#install.packages("quantreg")  
suppressMessages(suppressWarnings(library(quantreg)))  
fit_rq <- rq(outcome ~ group*age,data=df)
```

```
## Warning in rq.fit.br(x, y, tau = tau, ...): Solution may be nonunique
```

```
summary(fit_rq,se="nid")
```

```
##  

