## Coefficients:  
##           Value      Std. Error t value Pr(>|t|)  
## (Intercept) 34.64455   0.62947   55.03749 0.00000  
## group2      3.65202   1.23630    2.95398 0.00329  
## group3      8.70705   1.00415    8.67107 0.00000  
## age        -3.10804   0.82288   -3.77702 0.00018  
## group2:age -0.47171   1.46960   -0.32098 0.74837  

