## group3:age -1.31063   1.23464   -1.06155 0.28897
```

```
#https://www.rdocumentation.org/packages/aod/versions/1.3.1/topics/wald.test  
#install.packages("aod")  
suppressMessages(suppressWarnings(library(aod)))  
#https://www.rdocumentation.org/packages/Zelig/versions/5.1.7/topics/vcov_rq  
#install.packages("Zelig")  
suppressMessages(suppressWarnings(library(Zelig)))  
wald.test(b = coef(fit_rq), Sigma = vcov_rq(fit_rq), Terms = 5:6)
```

```

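### Does the plan need to add an interaction estimate and confidence interval for each pair of groups beside the Wald p-value?

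*Combined protocol and SAP*

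**What the plan says.** All references are to the combined protocol and SAP. Under *Statistical methods* the plan opens with "We will perform pairwise comparisons of the three groups, i.e., three comparisons". Heterogeneity is then handled as a significance question: "We will use quantile regression adjusted for site to test for significant interaction between the predefined dichotomized subgroups and treatment group", judged by a Wald test at 0.05.

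Estimation is assigned to a different tool: "We will quantify and report differences between the groups using Hodges-Lehmann median difference", with 98.3% intervals, and the subgroup analyses are to be shown in forest plots. The analyses are labelled exploratory and hypothesis-generating. On publication the plan says "All reports will be added as supplemental material in the final paper".

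The attached Supplemental Material is offered as an example of the planned analyses for one subgroup (age). Under *Quantile regression for interaction only* it fits "fit_rq <- rq(outcome ~ group*age,data=df") at the median and prints "group2:age -0.47171" (SE 1.46960) and "group3:age -1.31063" (SE 1.23464). It then runs "wald.test(b = coef(fit_rq), Sigma = vcov_rq(fit_rq), Terms = 5:6"), which gives a chi-square of 1.1 on 2 df and P = 0.57. Under *Hodges-Lemann median differences* it gives all three pairwise differences with 98.3% intervals in each age stratum.

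**The concern.** The stated objective is the intervention effect across subgroups, so the quantity of interest is how far a treatment difference changes from one stratum to the other. The text promises a test of that change but no estimate or interval. The example prints coefficients for group 2 versus 1 and 3 versus 1, without intervals, and nothing for 3 versus 2, although three pairwise comparisons are announced.

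A reader shown only P = 0.57 might conclude that age makes no difference. The example's own code suggests otherwise. It multiplies every outcome above age 65 by 0.9, so simulated differences of 3, 8 and 5 shrink by 0.3, 0.8 and 0.5. With the example's standard errors, the 2-df test has only about 8% power for an interaction of that size. If non-significance were read as equality, the subgroup paper could mislead whoever plans the next trial.

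**Working it through.** **Inputs.** Interaction coefficients and SEs as quoted. SE of the age coefficient 0.82288 (same table). Hodges-Lehmann estimates and 98.3% limits from the last section of the Supplemental Material, with signs reversed so that each reads as higher-numbered minus lower-numbered group.

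**1. Reproduce the Wald test.** The covariance of the two interaction terms is not printed. In a model with six separate group-by-age cells, the two terms share only the age contrast in group 1, so I take the covariance as 0.82288² = 0.677.

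- Variances: 1.46960² = 2.160 and 1.23464² = 1.524.
- Determinant: 2.160 × 1.524 − 0.677² = 2.834.
- X² = (0.47171² × 1.524 − 2 × 0.47171 × 1.31063 × 0.677 + 1.31063² × 2.160) / 2.834 = 1.133.
- P = exp(−1.133/2) = 0.567.

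This matches the printed 1.1 and 0.57. Varying the covariance from 0.3 to 1.1 keeps P between 0.52 and 0.57.

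**2. What the printed regression output already yields** (estimate ± 1.96 SE).

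- 2 versus 1: −0.47 ± 1.96 × 1.470, giving −3.35 to 2.41.
- 3 versus 1: −1.31 ± 1.96 × 1.235, giving −3.73 to 1.11.
- 3 versus 2: −1.31063 + 0.47171 = −0.84; SE = √(2.160 + 1.524 − 2 × 0.677) = 1.526, giving −3.83 to 2.15.

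The third pair needs one subtraction and the covariance from step 1.

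**3. What the planned Hodges-Lehmann output already yields.** The two age strata contain different patients, so their estimates are independent. Each SE is the half-width divided by 2.387 (the normal quantile for 98.3%). The SE of the difference is the root of the summed squares.

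| Pair | ≤65: estimate (half-width) | >65: estimate (half-width) | SE of difference | >65 minus ≤65 (95% CI) |
|---|---|---|---|---|
| 2 v 1 | 3.06 (2.10) | 3.20 (1.70) | √(0.878² + 0.712²) = 1.131 | +0.15 (−2.07 to 2.36) |
| 3 v 1 | 8.41 (1.85) | 7.29 (1.54) | √(0.775² + 0.646²) = 1.009 | −1.12 (−3.10 to 0.86) |
| 3 v 2 | 5.40 (2.09) | 4.07 (1.63) | √(0.876² + 0.683²) = 1.111 | −1.33 (−3.51 to 0.84) |

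In 1,500 data sets simulated from the example's code with its printed cell sizes, intervals built this way covered the true interaction 95.7%, 95.1% and 95.3% of the time.

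**4. Compare.** The 95% half-widths in step 3 are 2.22, 1.98 and 2.18, against 2.88, 2.42 and 2.99 in step 2. Both routes show plainly that P = 0.57 leaves sizeable interactions open.

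**The case for a change.** The strongest case for a change is that an interaction interval should not have to be reconstructed. Publishing raw output is not the same as planning a result, and the subtracted Hodges-Lehmann shifts are not the quantity the Wald test examines. In the example they give +0.15 for 2 versus 1, against −0.47 from the median regression, so even the sign differs. An interval table would come from models already fitted and would add no test.

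Part of this stands. The text promises neither an interaction interval nor the 3 versus 2 contrast, and the Hodges-Lehmann route is approximate. If the distributions differ by more than a shift, it also answers a slightly different question from the median regression. Under the example's code, however, both methods share one target, so the sign difference is sampling noise: +0.15 and −0.47 both lie well inside either interval.

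The power argument carries little weight. It describes invented data (SD 5, means 35, 38 and 43), says nothing about the variability or subgroup sizes of the real trial, and is unchanged by printing an interval. Nor does the p-value stand alone: sparse data would show as wide stratum intervals in the forest plots. The choice of interval would itself be a matter of convention, since the plan already uses 0.05 for the interaction and 98.3% for pairwise differences, and either level could be defended.

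The example model also lacks the site term that the text requires. That mismatch is separate, and an interval table would not resolve it.

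**Conclusion.** No change follows. The omission is one of presentation in a declared exploratory analysis. The planned test is valid as described, its example result reproduces (1.133 against 1.1; 0.567 against 0.57), and nothing in the plan says a non-significant test will be read as equal effects. Estimates with uncertainty for all three pairs can be recovered from planned and published output, with 95% half-widths of 2.0 to 2.2 in the example by the Hodges-Lehmann route and 2.4 to 3.0 from the regression. Statisticians who print the intervals beside the coefficients would be filling in a detail sensibly, not departing from the plan.

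This rests on three assumptions: the final reports follow the layout of the example; the unprinted covariance is as derived from the cell structure; and normal approximations are adequate. All magnitudes come from simulated data without site adjustment, so they illustrate the point and do not predict the trial's precision.
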